7.3 LOST TO FOLLOW-UP

A participant will be considered lost to follow-up if he or she fails to return for two or more visits and is unable to be contacted by the study site staff; if a subject is hospitalized outside the YNHHS we will attempt follow for clinical outcomes and concomitant medications.

The following actions must be taken if a participant fails to return to the clinic for a required study visit:

- The site will attempt to contact the participant and reschedule the missed visit within one day and counsel the participant on the importance of maintaining the assigned visit schedule and ascertain if the participant wishes to and/or should continue in the study.
- Before a participant is deemed lost to follow-up, the investigator or designee will make every effort to regain contact with the participant (where possible, 3 telephone calls and, if necessary, a certified letter to the participant's last known mailing address or local equivalent methods). These contact attempts should be documented in the participant's medical record or study file.
- Should the participant continue to be unreachable, he or she will be considered to have withdrawn from the study with a primary reason of lost to follow-up.

8 STUDY ASSESSMENTS AND PROCEDURES

8.1 EFFICACY ASSESSMENTS

Biological specimen collection and laboratory evaluations.

On study days 0, 2 (NP swab optional, saliva required), 4 (NP swab and saliva both required) and 6 (NP swab optional, saliva required), 14+/-2 (NP swab and saliva both required) and 28+/-2, (NP swab and saliva both required), samples will be obtained and analyzed by an FDA-authorized COVID-19 RT-PCR assay coordinated through the YNHH Clinical Virology Laboratory, and Yale Department of Pathology. Additional testing including antigen detection may be done on an NP swab, nasal swab or saliva.

On study days 0, 14+/-2 and 28+/-2, blood will be collected for 1) clinical surveillance→complete blood count, blood chemistries and coagulation including electrolytes, BUN, creatinine, AST, ALT, total and direct bilirubin, HS-CRP, LDH and alkaline phosphatase, PT, INR, d-dimer, fibrinogen; 2) research testing including obtaining serum, plasma and peripheral blood mononuclear cells for research studies. A maximum of 125 mL of blood will be requested to be collected on days 0, 14 and day 28 (total of 375 mL over four weeks) for these purposes.

Respiratory swab and saliva RT-PCR testing will be done by YNHHS or YNHHS-designated send-out laboratories. Quidel's Sofia platform will be use at the study site for antigen detection. Positivity and Ct values will be recorded and \log_{10} viral loads back-extrapolated from \log_{10} being equivalent to 3.3 Ct units or as determined using a concomitant standard curve.

Camostat mesylate in COVID-19 Outpatients

Protocol #2000027971

Version 8.0
18 August 2020

Blood chemistries and CBCs (and an FDA-approved POC urine pregnancy test will be done on site prior to enrollment for appropriate women as required) will be done by YNHHS laboratories and recorded, and results reported to patients.

Remaining blood samples will be stored in a biological specimen repository approved by Yale University as follows:

Investigator: [name]
Type of Review: Modification/Update
Title of Study: Specimen Repository for Hematologic Diseases
IRB Protocol ID: 1401013259
Submission ID: MOD00029770
Committee Name: IRB 0-Ad Hoc Committee

Final Approval Date: 3/29/2020

Expiration Date: 2/17/2021

Remaining respiratory tract samples (NP swabs, saliva) processed by the YNHH Virology laboratory will be overlabelled with unique identifiers (to de-identify the samples) and conserved for future use in the [name] laboratory which has been approved to handle such COVID-19 specimens by EH&S.

8.2 SAFETY AND OTHER ASSESSMENTS

At study visits, vital signs including pulse oximetry will be obtained. Physical examination will not be performed routinely on participants unless dictated by signs or symptoms. Any patient experiencing symptoms requiring medical examination will be referred to hospital..

On all study days, participants will be asked to answer specific questions that relate to known potential adverse effects of camostat mesylate. The previously determined incidence of adverse effects (when drug administered for at least two weeks) are:

Symptom	0.1 to 0.5%	<0.1%	
Rash	0.4		
Pruritus	0.2%		
Gastrointestinal	0.1 to 0.5% (nausea, abdominal discomfort or fullness, diarrhea)	Anorexia, vomiting, dry mouth, heartburn, abdominal pain, constipation	

Included in the informed consent form are concerns about rare side effects. Study personnel will specifically elicit whether there are symptoms concerning for severe allergy such as jaundice, anaphylaxis or anaphylactoid reactions will be determined on a daily basis by study personnel who will ask about such symptoms (yellow eyes, weakness, wheezing, shortness of breath, tongue swelling, hives, rash) during the first 7 days of the study. Laboratory evidence of adverse effects such as thrombocytopenia, hyperbilirubinemia, or hyperkalemia will only be able to be determined at day 14.

Participants will be informed on study day 28 of all available research-specific study results to date. Results that return after day 28 will be communicated with the participant within 2 weeks of such results. If there are actionable results of routine/standard of care lab tests including CBC, chemistries and coagulation studies, they will be reported to participants in a timely manner, otherwise they will be discussed at the day 28 visit or if they become available after day 28, within 2 weeks of when new results become available.

8.3 ADVERSE EVENTS AND SERIOUS ADVERSE EVENTS

The Common Terminology Criteria for Adverse Events (CTCAE) Version 5.0 will be used to characterize adverse events.

The study involves a repurposed drug in routine clinical use in Japan and is an investigational new drug in the United States.

The study involves the use of placebo in a population with diagnosed COVID-19, which is justified because there is no drug approved for its treatment, nor is there a current outpatient study for treatment of diagnosed COVID-19.

8.3.1 DEFINITION OF ADVERSE EVENTS (AE)

Adverse event means any untoward medical occurrence associated with the use of an intervention in humans, whether or not considered intervention-related (21 CFR 312.32 (a)).

Adverse events in this study will be assessed by verbal report, and specifically sought according to the approval package insert.

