Others	-	Edema	-
		Hypoglycemia	

Table 1. Summary of Safety Data for Camostat Mesylate tablets

Data summarized from the use of camostat mesylate for the indications of "Remission of acute symptoms of chronic pancreatitis" (83 ARs including abnormal lab.values observed in 69 (1.8%) of 3,806 patients) and "Postoperative reflux esophagitis" (75 ARs including abnormal lab.values observed in 57 (1.3%) of 4,224 patients).

Additional clinically significant ARs that may occur (incidences unknown*):

Shock or anaphylactoid symptoms, thrombocytopenia, hepatic function disorder or jaundice, hyperkalaemia.

*Incidence unknown: ADRs classified and collected from spontaneous reports.

Two case reports have been found. One about autoimmune hepatitis that may have occurred following drug-induced liver injury that may have been related to camostat treatment. Stopping the drug did not lead to complete remission, but low dose of corticosteroids completely cured the liver function¹⁷. Another case study reported eosinophilic pneumonia probably caused by 10 days treatment with camostat. The peripheral blood eosinophilia and eosinophilic infiltration into the alveolar space improved with the cessation of the drug¹⁸.

Relevant monitoring of treatment is based on the knowledge about the reported clinically significant adverse reactions, which comprises: hyperkalemia, hepatic function disorder or jaundice, thrombocytopenia, eosinophilic pneumonia and shock/anaphylactic symptoms.

Safety in patients with reduced renal output or end-stage renal disease

Human data on camostat mesylate treatment and renal insufficiency.

Three studies have been found in Medline and/or Embase that address the safety of camostat mesylate administration in patients with renal insufficiency:

1. Onbe et al. J Diabet Complications 1991;5:167-8. 8 pts with nephrotic syndrome and diabetic nephropathy. CM 600 mg daily for 4 weeks. Reduced proteinuria, creatinine clearance stable throughout study.

2. Ikeda et al. J Diabetes Complications 1999;13:56-8

3 pts with nephrotic syndrome and diabetic nephropathy. CM 600 mg daily for 4 weeks. Reduced proteinuria, no side effects reported.

3. Matsubara et al. Clin Nephrol 1989;32:119-23

17 pts with heavy proteinuria caused by varous nephropathies. CM 600 mg daily for 4 weeks. Urine protein excretion diminished from week 2. No changes in serum creatinine during or after the study.

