3 OBJECTIVES AND ENDPOINTS

OBJECTIVES	ENDPOINTS	JUSTIFICATION FOR ENDPOINTS
Primary To determine whether camostat mesylate reduces SARS-CoV-2 viral load within 2-3 days after laboratory-confirmed diagnosis of COVID-19 disease in ambulatory patients.	Primary Endpoint: 1. Change (reduction) from baseline to day 4 in respiratory (Nasopharyngeal swab, saliva RT-PCR) \log_{10} viral load .	Per FDA recommendations and our own judgment, the timing of this primary endpoint was chosen because reduction of viral load in respiratory tract samples would be expected to be associated with anti-viral activity of the study drug, and would be expected to be associated with continued reduction of viral load during drug administration, hence potential reduction severity of COVID-19 disease and reduction of transmission by reducing infectiousness of infected individual. If we are able to achieve a reduction in viral load then a trial with clinical endpoints such as risk for progression to hospitalization and/or need for intensive unit care would be justified.
Secondary 1. To determine whether camostat mesylate reduces SARS-CoV-2 viral load within 7 days after laboratory-confirmed diagnosis of COVID-19 disease in ambulatory patients.	1. Change from baseline to day 2 and to day 6 in respiratory (Nasopharyngeal swab, saliva RT-PCR) \log_{10} viral load. 2. Difference in rate of positive COVID-19 test at day 6, 14 and 28	As for the primary endpoints (above). We expect to see a time-dependent reduction of viral load, hence the second time point.

Camostat mesylate in COVID-19 Outpatients

Protocol #2000027971

Version 8.0
18 August 2020

OBJECTIVES	ENDPOINTS	JUSTIFICATION FOR ENDPOINTS
2. To determine the effect of camostat mesylate on COVID-19 symptom score. 3. To evaluate the safety of camostat mesylate 4. Adverse events	3. Change of COVID-19 symptom score from baseline, to days 6 and 14 Assessment of safety by labs and history and physical, according to The Common Terminology Criteria for Adverse Events (CTCAE) Version 5.0.	We expect to see a reduction in symptom score from baseline at day 6 and day 14 +/-. If the secondary endpoints are not achieved, then a trial to examine the effect of camostat mesylate on COVID-19 would not be justified.
Tertiary/Exploratory		

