8.3.4 TIME PERIOD AND FREQUENCY FOR EVENT ASSESSMENT AND FOLLOW-UP

The occurrence of an adverse event (AE) or serious adverse event (SAE) may come to the attention of study personnel during study visits and interviews of a study participant presenting for medical care, or upon review by a study monitor.

All AEs including local and systemic reactions not meeting the criteria for SAEs will be captured on the appropriate case report form (CRF). Information to be collected includes event description, time of onset, clinician's assessment of severity, relationship to study product (assessed only by those with the training and authority to make a diagnosis), and time of resolution/stabilization of the event. All AEs occurring while on study must be documented appropriately regardless of relationship. All AEs will be followed to adequate resolution.

Any medical condition that is present at the time that the participant is screened will be considered as baseline and not reported as an AE. However, if the study participant's condition deteriorates at any time during the study, it will be recorded as an AE.

Changes in the severity of an AE will be documented to allow an assessment of the duration of the event at each level of severity to be performed. AEs characterized as intermittent require documentation of onset and duration of each episode.

Study personnel will record all reportable events with start dates occurring any time after informed consent is obtained until 7 (for non-serious AEs) or 30 days (for SAEs) after the last day of study participation. At each study visit, the investigator will inquire about the occurrence of AE/SAEs since the last visit. Events will be followed for outcome information until resolution or stabilization.

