9.4.4 SAFETY ANALYSES

Safety will be reported by treatment arm using descriptive statistics (means and standard deviations or frequencies and counts) and assessed by comparing the adverse events in the treatment group using Type I error of 5% (2-sided); no control for multiplicity will be done for safety outcomes. We will consider Wilcoxon rank sum tests or two-sample t-tests for continuous outcomes and the exact binomial distribution for proportions.

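### Section 8.3.1 finds adverse events by verbal report, while Sections 3 and 8.2 rely on blood tests, so symptomless laboratory harms are not assured of entering the adverse-event comparisons

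*Combined protocol and SAP*

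**What the plan says.** Section 8.3.1 first defines an adverse event broadly, as any untoward medical occurrence. It then says how events are found: "Adverse events in this study will be assessed by verbal report, and specifically sought according to the approval package insert". Section 8.2 describes specific questions on known side effects. Its incidence table covers rash, pruritus and gastrointestinal symptoms, and daily questions about allergy and jaundice run through the first seven days.

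Other sections rely on blood tests:

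- Section 3, safety endpoint: "Assessment of safety by labs and history and physical, according to The Common Terminology Criteria for Adverse Events (CTCAE) Version 5.0".
- Section 2.2, monitoring targets: "hyperkalemia, hepatic function disorder or jaundice, thrombocytopenia, eosinophilic pneumonia and shock/anaphylactic symptoms".
- Section 8.2: "Laboratory evidence of adverse effects such as thrombocytopenia, hyperbilirubinemia, or hyperkalemia will only be able to be determined at day 14".
- Section 8.1: "On study days 0, 14+/-2 and 28+/-2, blood will be collected for 1) clinical surveillance". The panel includes a blood count, electrolytes, AST, ALT and bilirubin.

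For analysis, Section 9.4.4 reports safety with "descriptive statistics (means and standard deviations or frequencies and counts) and assessed by comparing the adverse events in the treatment group", at a two-sided 5% level. It considers a t-test or Wilcoxon test for continuous outcomes and an exact binomial method for proportions. At the interim, Section 9.4.6 names only the adverse-event rate as its safety comparison.

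**The concern.** Of the five monitoring targets in Section 2.2, hyperkalemia and thrombocytopenia are defined by a blood test, and hepatic function disorder largely so. All three can be present without complaint. If staff follow the ascertainment sentence in 8.3.1, a participant with a severe value and no symptoms may not be recorded as having an adverse event. Another participant with the same value may be recorded because an investigator judged it to be one.

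Safety is a secondary endpoint, and Section 2.1 says that success would lead to larger trials, including prophylaxis. A safety comparison that leaves open whether the named laboratory harms are counted is a weak basis for that step. The point is about how such harms are found and counted, not about when blood is drawn.

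**Working it through.** **1. Can a laboratory value become an adverse event under the text?**

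| Section | What it provides | Does it make an abnormal value an adverse event? |
|---|---|---|
| 8.3.1 | Verbal report, plus events sought per the package insert | Not stated; the insert's reactions include laboratory values |
| 8.2 | Symptom questions; names laboratory evidence of adverse effects at day 14 | Implied, no recording rule |
| 8.3.4 | Events surface at visits, interviews or monitor review; all must be documented | Applies once something is judged an event |
| 8.3 and 8.3.3.1 | CTCAE v5.0 characterizes adverse events | Grades events already found |
| 3 | Safety by laboratory tests under CTCAE | Implied, no recording rule |
| 9.4.4 | Means and SDs, or frequencies and counts | Counts allowed; no threshold, grade or shift defined |
| 9.4.6 | Adverse-event rate | Depends wholly on the rows above |

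Sections 8.3.8 (events of special interest) and 9.4.8 (tabulation of individual data) are marked not applicable, so neither supplies a listing in which extreme values would appear.

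**2. What would tests on continuous values show?** The plan gives no figure for this, and no laboratory means or SDs. The 57 per arm is from Section 9.2; every other input is assumed.

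Platelets: mean 220, SD 60 in both arms, with k treated participants replaced by values near 50 (SD 10).

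- Shift in arm mean for k = 3: 3 × (220 − 50)/57 = 8.9.
- Standard error of the difference: 60 × √(2/57) = 11.2.
- Share of 4,000 simulated trials with two-sided p < 0.05: k = 3, 9% (t) and 7% (Wilcoxon); k = 5, 18% and 11%.

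A second set of assumptions gives the same picture:

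- Platelets with mean 230, SD 60 and three values at 40: shift 3 × 190/57 = 10.0; about 10% (t) and 6% (Wilcoxon).
- Potassium with mean 4.2, SD 0.4 and three values at 6.5: shift 3 × 2.3/57 = 0.12; 16% and 8%.

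**3. Would counting cases give more power?** For k cases v 0 with 57 per arm, the two-sided Fisher p is 2 × C(57,k)/C(114,k). For k = 3 this is 2 × (57 × 56 × 55)/(114 × 113 × 112) = 2 × 175,560/1,442,784 = 0.243.

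| Cases v 0 | 2 | 3 | 4 | 5 | 6 |
|---|---|---|---|---|---|
| Fisher p | 0.496 | 0.243 | 0.118 | 0.057 | 0.027 |

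Six against none are needed to pass 5%. Under the first platelet assumptions, comparing counts below a cut-off by Fisher's test is significant in about 1% (cut-off 75) or 5% (cut-off 150) of trials with three cases, and about 19% or 12% with five. That is no systematic gain over the t-test.

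**The case against.** A reader might infer that laboratory harms can never enter the adverse-event comparison and will appear only as means. The documents do not support that.

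- The sentence in 8.3.1 also has events sought according to the package insert, and the insert's reactions include laboratory findings: Section 2.2 reports "83 ARs including abnormal lab.values observed in 69 (1.8%) of 3,806 patients".
- Section 8.3.4 sets no limit to complaints: "All AEs occurring while on study must be documented appropriately regardless of relationship". It also records deterioration from baseline as an adverse event.
- Section 8.3.2 gives blood dyscrasias as an example of a serious event.
- Section 9.4.4 allows frequencies, counts and an exact method for proportions, and the Wilcoxon test is not a comparison of means.
- The schedule of activities puts adverse-event review at the same day-14 and day-28 visits as the blood tests. Section 10.1.6 gives the DSMB safety data by arm under a charter that is to define its data elements.

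All of this stands, and a careful investigator could well record a severe platelet value. It does not close the gap. The duty to document applies once something has been identified as an adverse event, and a proportion needs a defined event. Section 8.2's own questions do not reach the blood-based items.

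It is also fair to object that the fix adds no power, and that recording every grade shift would mix trivial changes with severe ones in acutely ill patients. Both points are accepted.

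**Conclusion.** The concern holds in a limited form. Sections 3, 8.2 and 8.3.1 disagree on how adverse events are ascertained, so inclusion of symptomless laboratory harms depends on individual judgment. This is more than a missing detail, because the interim safety comparison rests on the adverse-event rate alone.

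How many cases would be missed cannot be computed from the documents. The simulated percentages rest on assumed platelet and potassium distributions and illustrate only that a few extreme values are hard to see in a test on continuous data. What would be gained is uniform recording and severe cases that a DSMB can see by arm and weigh, not statistical significance.

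**What to change.** Reconcile 8.3.1 with Sections 3 and 8.2, for example: adverse events will be ascertained from verbal report and from the scheduled day-14 and day-28 laboratory tests, with laboratory values graded by CTCAE v5.0. The investigators should state in advance which change in grade is recorded as an adverse event; not every shift need be one.

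In 9.4.4 add a table by arm of day-0 grade against worst post-baseline grade for platelets, potassium, AST, ALT and bilirubin. Give the number of participants worsening in grade, with a confidence interval for the comparison between arms.

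The cost is a short change of text and one table, with no new sampling. The downside is some extra records, part of them due to COVID-19 itself; the placebo arm gives the comparison for those.

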8.3.2 DEFINITION OF SERIOUS ADVERSE EVENTS (SAE)

An adverse event (AE) or suspected adverse reaction is considered "serious" if, in the view of either the investigator or sponsor, it results in any of the following outcomes: death, a life-threatening adverse event, inpatient hospitalization or prolongation of existing hospitalization, a persistent or significant incapacity or substantial disruption of the ability to conduct normal life functions, or a congenital anomaly/birth defect. Important medical events that may not result in death, be life-threatening, or require hospitalization may be considered serious when, based upon appropriate medical judgment, they may jeopardize the participant and may require medical or surgical intervention to prevent one of the outcomes listed in this definition. Examples of such medical events include allergic bronchospasm requiring intensive treatment in an emergency room or at home, blood dyscrasias or convulsions that do not result in inpatient hospitalization, or the development of drug dependency or drug abuse.

8.3.3 CLASSIFICATION OF AN ADVERSE EVENT

8.3.3.1 SEVERITY OF EVENT

The Common Terminology Criteria for Adverse Events (CTCAE) Version 5.0 will be used to characterize adverse events.

For adverse events (AEs) not included in the protocol defined grading system, the following guidelines will be used to describe severity.

- **Mild** – Events require minimal or no treatment and do not interfere with the participant's daily activities.
- **Moderate** – Events result in a low level of inconvenience or concern with the therapeutic measures. Moderate events may cause some interference with functioning.
- **Severe** – Events interrupt a participant's usual daily activity and may require systemic drug therapy or other treatment. Severe events are usually potentially life-threatening or incapacitating. Of note, the term "severe" does not necessarily equate to "serious".

8.3.3.2 RELATIONSHIP TO STUDY INTERVENTION

All adverse events (AEs) must have their relationship to study intervention assessed by the clinician who examines and evaluates the participant based on temporal relationship and his/her clinical judgment. The degree of certainty about causality will be graded using the categories below. In a clinical trial, the study product must always be suspect.

- **Related** – The AE is known to occur with the study intervention, there is a reasonable possibility that the study intervention caused the AE, or there is a temporal relationship between the study intervention and event. Reasonable possibility means that there is evidence to suggest a causal relationship between the study intervention and the AE.
- **Not Related** – There is not a reasonable possibility that the administration of the study intervention caused the event, there is no temporal relationship between the study intervention and event onset, or an alternate etiology has been established.

